later without further practice (Retest 2). Each block consists of 50 key presses (ideally 10 sequences) and is followed by a rest block of 15-20 seconds without finger tapping. A two-minute rest period will be implemented after 14 blocks to further minimize the effects of fatigue on the last 4 blocks that are used to calculate the primary outcome. Performance on the MSL will be assessed using the 'Performance Index (PI)' [$PI = \exp^{-(\text{seqDur}(x))} * \exp^{-(\text{Errors}(x)/12)} * 100$], whereby (x) represents the blocks of the trials (King et al. 2017b). Given that both speed and accuracy determine the PI, these measures will be explored. During the single-task condition, participants view a fixation cross in the middle of the screen with the sequence presented above.

The primary outcome for experiment 1 will be the offline consolidation, measured as the change in PI between the first 4 blocks at Retest 1 immediately after the nap or wake intervention and the last 4 blocks of Learning immediately prior to the intervention. The primary outcome for experiment 1 will be analyzed with a repeated measures analysis of variance with the following factors and conditions: 4 blocks * 2 sessions (end of learning/begin of retest 1) * 2 groups (nap/wake) * 2 populations (pwPD/controls). Linear mixed models will be considered depending on the presence of missing values and interactions with covariates (age, gender, disease severity and levodopa equivalence dose) will be analyzed.

Experiment 2: The design of experiment 2 is similar to experiment 1, except that participants will learn two motor sequences that are visually and auditory cued by means of a serial reaction time task (SRT). After learning both sequences, participants will nap for 2 hours, but this time while the melody of one of the two sequences will be replayed using auditory TMR. Performance on both sequences will be re-assessed immediately after the intervention (Retest 1), and again at 24h retention (Retest 2) without cues.

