The primary outcome for experiment 2 is the 'offline consolidation' defined as the change in PI between the first 4 blocks at retest immediately after the nap and the last 4 blocks at learning prior to the intervention, which will be compared between the sequence that was replayed during the nap (replay) and the sequence that was not replayed (no-replay). The primary outcome for experiment 2 will be analyzed with a repeated measures analysis of variance with the following factors and conditions: 4 blocks * 2 sessions (end of learning/begin of retest 1) * 2 sequences (replay/no-replay) * 2 groups (pwPD/controls). Linear mixed models will be considered depending on the presence of missing values and interactions with covariates (age, gender, disease severity and levodopa equivalence dose) will be analyzed.

Secondary outcomes

All other comparisons for experiments 1 and 2 are considered secondary in importance. The PI is used as the main dependent variable of interest for all secondary outcomes listed below, which will be compared across the two intervention groups (Nap/Wake) and two study populations (pwPD/Controls). An MSL with consecutive dual task condition is performed for an additional 4 blocks at learning, immediately after the intervention (Retest 1) and again after

24hrs of retention (Retest 2). The following comparisons will be analyzed for both experiments.

Single task performance (PI):

1. Retention, measured as the change in PI between the first 4 blocks at Retest 2 compared to the last 4 blocks at Retest 1.
2. Learning slope over 14 blocks during learning, prior to the intervention.
3. Learning slope over 14 blocks after the 24hr retention period (Retest 2)
4. End of learning performance assessed over the last 4 blocks during learning prior to the intervention (Learning)
5. Post-extensive practice performance assessed over the last 4 blocks immediately after the intervention (Retest 1)

Dual tasking performance (PI):

1. Offline consolidation measured as the change in PI between the 4 blocks of dual tasking at Retest 1 immediately after the intervention compared to the 4 blocks of dual tasking during learning for experiment 1, and differences on PI between sequences A and B during the 4 blocks at Retest 1 for experiment 2.

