2. Retention, measured as the change in PI between the 4 blocks of dual tasking at Retest 2 compared to the 4 blocks of dual tasking at Retest 1 for experiment 1, and differences on PI between sequences A and B during the 4 blocks at Retest 2 for experiment 2.
3. Learning performance over the 4 blocks of dual tasking during learning prior to the intervention for experiment 1 only.
4. Learning performance over the 4 blocks of dual tasking immediately after the intervention (Retest 1) for both experiments.
5. Learning performance over the 4 blocks of dual tasking after the 24hr retention period (Retest 2) for both experiments.

Dual task cost (Δ PI), i.e. the difference in PI between 4 blocks of dual tasking and 4 blocks of single tasking.

1. Offline consolidation measured as the change in Δ PI between Retest 1 immediately after the intervention (4 blocks of dual tasking versus last 4 blocks of single tasking) and the Δ PI during learning (4 blocks of dual tasking versus the first 4 blocks of single tasking) for experiment 1, and difference in Δ PI between sequences A and B (4 blocks of dual tasking versus last 4 blocks of single tasking) at Retest 1 for experiment 2.
2. Retention, measured as the change in Δ PI between Retest 2 (4 blocks of dual tasking and last 4 blocks of single tasking) and Retest 1 (4 blocks of dual tasking and last 4 blocks of single tasking) for experiment 1, and difference in Δ PI between sequences A and B (4 blocks of dual tasking versus last 4 blocks of single tasking) at Retest 2 for experiment 2.
3. Learning performance assessed as the Δ PI of the 4 blocks of dual tasking and first 4 blocks of single tasking during learning for experiment 1 only.
4. Post extensive practice assessed as the Δ PI of the 4 blocks of dual tasking and last 4 blocks of single tasking immediately after the intervention (Retest 1) for both experiments.

5. Post extensive practice assessed as the Δ PI of the 4 blocks of dual tasking and last 4 blocks of single tasking after the 24hours retention period (Retest 2) for both experiments.

Control comparisons (PI): For experiment 2, four additional comparisons will be analyzed to ensure that participants could learn both sequences equally well. The two sequences can be labeled as either (sequence A / sequence B), irrespective of which sequence was replayed during the nap period, or as (replay / no-replay) respective of the sequence that was replayed during the nap period.

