1. End of learning performance on sequence A and B will be assessed as the difference in PI between the last 4 blocks of sequence A and the last 4 blocks of sequence B during learning prior to the intervention.
2. Learning slopes of sequence A and B will be assessed as the difference in PI between the first 14 blocks of sequence A and the first 14 blocks of sequence B during learning prior to the intervention.
3. End of learning performance on the replay and no-replay sequences will be assessed as the difference in PI between the last 4 blocks of the TMR sequence and the last 4 blocks of the control sequence during learning prior to the intervention.
4. Learning slopes of the replay and no-replay sequences will be assessed as the difference in PI between the first 14 blocks of sequence A and the first 14 blocks of sequence B during learning prior to the intervention.

Tertiary outcomes

Experiment 1 - Motor Execution Test (MET)

Participants perform a self-initiated MET by tapping a simple 4-element (i.e. 4-3-2-1) finger sequence presented on screen as rapidly and accurately as possible with their non-dominant hand for 4 blocks during learning and again for 4 blocks at each retest assessment. Each block consists of 52 key presses (ideally 13 sequences) and is followed by a rest block of 15-20 seconds without finger tapping. Performance on the MET will be compared between Retest 1 and learning and between Retest 2 and Retest 1.

Experiment 2 - Random Serial Reaction Time task (random SRT)

Participants will perform random sequences that are visually cued by means of a SRT for 4 blocks at learning and again at each retest assessment. Each block consists of 50 key presses and is followed by a rest block of 15-20 seconds without finger tapping. Performance on the random SRT will be compared between Retest 1 and learning and between Retest 2 and Retest 1.

Psychomotor Vigilance Test (PVT):

The MSL (Experiment 1) and SRT (Experiment 2) tests will be preceded by a 10-minute PVT as an objective measure of the participants' vigilance prior to testing. The PVT will be presented on a laptop and subjects will be instructed to press a button as quickly as possible each time a visual stimulus is presented in the middle of the screen. Changes in PVT performance (number of lapses in attention defined as response times \geq twice the median response time) will be

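### The Experiment 2 primary model omits which sequence (A or B) was replayed, so any A-B difference in offline change stays in the error term

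*SAP*

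**What the plan says.** Under Primary outcome, Experiment 2, the SAP specifies a repeated measures ANOVA whose factors are block, session and "2 sequences (replay/no-replay) * 2 groups (pwPD/controls". The outcome is the change in PI from the last 4 learning blocks to the first 4 retest blocks, "which will be compared between the sequence that was replayed during the nap (replay) and the sequence that was not replayed (no-replay". Linear mixed models are held in reserve for missing values, and "interactions with covariates (age, gender, disease severity and levodopa equivalence dose) will be analyzed".

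During the nap "the melody of one of the two sequences will be replayed using auditory TMR". The SAP does not say how often A and how often B is the replayed one.

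Under Control comparisons (PI), the SAP recognises both ways of naming the sequences: "The two sequences can be labeled as either (sequence A / sequence B), irrespective of which sequence was replayed during the nap period". The alternative is to name them by replay status. Four comparisons are planned to check that both sequences were learned equally well. All four use data from the learning session. The first, for example, is a "difference in PI between the last 4 blocks of sequence A and the last 4 blocks of sequence B during learning prior to the intervention".

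**The concern.** Each participant contributes one replay-minus-no-replay contrast. For some it is A minus B, for the others B minus A. If A and B differ in how much they change over the nap for reasons unrelated to replay, that difference enters the contrast with a plus sign for one subset and a minus sign for the other. The planned model has no term to absorb it, so it counts as residual variation although its source is recorded.

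Such a difference is plausible because PI is exponential in sequence duration. Suppose, for illustration, that one sequence takes 0.2 s longer and error counts are equal. The same gain in seconds then produces a PI change only exp(-0.2) = 0.82 times as large. An ordinary difference in difficulty can therefore become a difference in offline change on the PI scale.

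At stake is the precision of the one contrast on which Experiment 2 rests, with a target of 20 participants per population.

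**Working it through.** **The plan's own figure.** Power calculation starts from 16 per group and allows 20% for dropout: 16/(1-0.20) = 20, and 16 x 1.2 = 19.2, rounded up to 20. Both give the stated 20 per population. No effect size or SD is given, so the 16 itself cannot be reproduced, and 80% power serves below as a benchmark.

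**Inputs.** From the SAP: model factors, alpha 0.05, power 0.80, 16 to 20 per population (32 to 40 in all). Assumed: a two-sided test; delta from 0 to 1 SD; the replay splits shown.

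**Model.** For participant i, let D_i be the replay minus no-replay change:

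D_i = tau + s_i*delta + e_i

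Here s_i = +1 if A was replayed and -1 if B was, delta is the A-B difference in offline change, and SD(e) = 1. A constant A-B level difference is the same before and after the nap, so it drops out of D_i. Simulating a 1 SD level difference gave bias 0.00 and type I error 0.049-0.051 at splits of 50:50, 60:40 and 70:30.

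**Balanced split, factor omitted.** The mean of D_i is tau, so there is no bias. The variance seen by the test is about 1 + delta^2. The standardised effect that gives 80% power at delta = 0 is 0.749 for n = 16, 0.66 for n = 20, 0.51 for n = 32 and 0.45 for n = 40. Dividing it by sqrt(1 + delta^2) and using the noncentral t gives the third column. The fourth and fifth columns simulate fixed equal halves.

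| delta (SD) | 1 + delta^2 | Power, noncentral t | Power, simulated | Type I error, simulated |
|---|---|---|---|---|
| 0 | 1.00 | 0.80 | 0.80 | 0.050 |
| 0.25 | 1.06 | 0.776 | 0.78 | 0.044 |
| 0.5 | 1.25 | 0.708 | 0.72 | 0.029 |
| 0.75 | 1.56 | 0.611 | 0.62-0.63 | 0.015 |
| 1.0 | 2.00 | 0.509 | 0.49-0.50 | 0.006 |

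The results hardly depend on n. Type I error falls below 0.05 because delta cancels from the mean while still inflating the estimated standard error.

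**Factor included.** The residual variance returns to 1 with n-2 df. Power is 0.796 at n = 16, 0.798 at n = 20 and 0.799 at n = 32 or 40, and type I error is about 0.05 for every delta.

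**Uneven split, factor omitted.** The shift in the replay estimate is delta*(nA-nB)/n:
- 8/8: 0
- 9/7: (2/16)*delta = 0.125*delta, or 0.06 SD at delta = 0.5
- 10/6: (4/16)*delta = 0.25*delta

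If 20 people start at 10/10 and 4 drop out irrespective of sequence, these splits have probability 2025/4845 = 0.42, 2400/4845 = 0.50 and 420/4845 = 0.09. If the split were instead left to simple randomisation, 60:40 or worse would occur with probability 0.50 for n = 20 and 0.27 for n = 40. As a stress case, a 70:30 split with delta = 0.5 gives type I error of 0.096 (n = 20) or 0.174 (n = 40).

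**The case against.** The strongest reply is that a within-person comparison of change scores already removes the obvious threat, a sequence that is simply harder. That stands for a constant difference in PI level. A reader might infer that any A-B difference harms the analysis; the SAP does not support that, because its primary outcome is a change.

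Second, the size is assumed. At delta = 0.25 the loss is about 2 points of power. Delta = 0.5 means that A-replayed and B-replayed participants differ by 2 x 0.5 = 1 SD in the mean replay contrast, and nothing in the SAP shows a difference that large. This also stands.

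Third, a reader might infer that the replay effect is biased. That needs an uneven split, and allocation may be set out in the protocol, which was not available. With a balanced split the test is valid and conservative. Under randomised replay, an imbalance gives a chance shift conditional on the realised split, not a systematic one. Dropout has limited reach: starting from 10/10, it cannot produce 12/8.

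Fourth, the SAP does address sequence equivalence through its four control comparisons. They do not answer this point: they use only pre-nap learning data, none examines offline change, and none enters the primary model. A non-significant result in 32 to 40 people would not establish equality.

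Balanced replay would therefore remove the bias but not the lost efficiency.

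**Conclusion.** The point holds as a matter of efficiency. The primary model leaves out a recorded source of variation that can be removed at almost no cost. With a balanced split and an assumed delta of 0.25 to 0.75 SD, power falls from 80% to between about 78% and 61-63%; including the factor keeps it at about 80%. A shift in the estimate is conditional on an uneven split among those analysed, and it would be small (at most 0.125*delta in about 91% of cases) if allocation is 10/10 and four people drop out irrespective of sequence. The size of delta, the split and the two-sided test are assumptions. The SAP does not support reading this as an invalid test, a demonstrated bias or a failure to counterbalance.

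**What to change.** In the Experiment 2 primary analysis, add replayed sequence (A or B) as a between-participant factor with its interaction with session x sequence. If the mixed model is used, the equivalent is an A/B identity x session term. Report the replay effect averaged with equal weight over A-replayed and B-replayed participants, and give the number of each analysed in each population. The control comparisons can stay as descriptive checks.

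The cost is one sentence in the SAP and about 1 df per population (power 0.796-0.799 instead of 0.80 if delta is zero), with cells of about 8 to 10 people under an even split. No new data are needed. The term should be fixed before results are seen, because adding it later would be a post hoc choice.

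### Four Experiment 2 dual-task outcomes, and control comparison 4, are defined on sequence A versus B, labels that ignore replay, so the dual-task outcomes do not isolate the TMR effect

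*SAP*

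**What the plan says.** Under Control comparisons (PI), the SAP sets out two ways to label the two Experiment 2 sequences. They can be "labeled as either (sequence A / sequence B), irrespective of which sequence was replayed during the nap period", or they can be labelled replay/no-replay according to what was played during the nap.

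The Experiment 2 primary outcome uses the second system: offline consolidation is "compared between the sequence that was replayed during the nap (replay) and the sequence that was not replayed (no-replay"), and the ANOVA factor is replay/no-replay.

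Four secondary outcomes use the first system for Experiment 2:

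- Dual tasking performance, item 1 (offline consolidation): "differences on PI between sequences A and B during the 4 blocks at Retest 1 for experiment 2"
- Dual tasking performance, item 2 (retention): "differences on PI between sequences A and B during the 4 blocks at Retest 2 for experiment 2"
- Dual task cost, item 1 (offline consolidation): "difference in Δ PI between sequences A and B (4 blocks of dual tasking versus last 4 blocks of single tasking) at Retest 1"
- Dual task cost, item 2 (retention): "difference in Δ PI between sequences A and B (4 blocks of dual tasking versus last 4 blocks of single tasking) at Retest 2"

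Control comparison 4 mixes the two systems: "Learning slopes of the replay and no-replay sequences will be assessed as the difference in PI between the first 14 blocks of sequence A", set against the same blocks of the other sequence, B.

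The introduction to Secondary outcomes says of the PI outcomes, for both experiments, "which will be compared across the two intervention groups (Nap/Wake) and two study populations (pwPD/Controls").

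**The concern.** Offline consolidation and retention are the outcomes on which a TMR effect under dual tasking should show. An A-B difference mainly measures whether one sequence is easier than the other. A real dual-task TMR effect could be missed, or a difficulty difference could be reported under the name of consolidation or retention.

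No other dual-task outcome fills the gap. Items 4 and 5 in both dual-task lists name no sequence contrast. The introduction offers only Nap/Wake and population, and everyone in Experiment 2 naps.

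Control comparison 4 raises a different issue. It is measured before the nap, so there is no TMR effect for it to miss. Its fault is that its definition repeats comparison 2. The four announced control comparisons are then only three distinct ones, and no definition compares the pre-nap learning slope between the replay and no-replay sequences.

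**Working it through.** **Which label each definition uses**

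| Experiment 2 item | Label used | Label its purpose needs |
|---|---|---|
| Primary outcome and model | replay/no-replay | replay/no-replay |
| Dual-task PI 1 and 2 | A/B | replay/no-replay |
| Dual-task cost 1 and 2 | A/B | replay/no-replay |
| Control 1 and 2 | A/B | A/B |
| Control 3 | TMR/control sequence | replay/no-replay |
| Control 4 | heading replay/no-replay, definition A/B | replay/no-replay |

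The count is 2 + 2 = 4 secondary outcomes, plus 1 of 4 control comparisons.

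**What A-B estimates.** For participant i, let r = +1 if A was replayed and -1 if B was. Then

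- A - B = s + r·d + e, so E[A - B] = s + (2p - 1)d.
- Replay - no-replay = r·(A - B), so its expectation is d + (2p - 1)s.

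With s = 0, A-B recovers 0 at p = 0.5, 0.2d at p = 0.6, 0.5d at p = 0.75 and d at p = 1. With p = 0.5, replay minus no-replay recovers d whatever s is.

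**Illustration.** The SAP gives no values for p, s or d, so all three are assumed; s and d are in SD of the paired difference (e has SD 1). The sample size is 32 (2 × 16) or 40 (2 × 20, the recruitment target), both from the Power calculation section. The test is a one-sample t test at two-sided 0.05 with an exact split at p, over 20,000 runs per cell.

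| n | p | s | d | A-B significant | Replay vs no-replay significant |
|---|---|---|---|---|---|
| 32 | 0.5 | 0 | 0.3 | 4% | 38% |
| 32 | 0.5 | 0 | 0.5 | 3% | 79% |
| 32 | 0.5 | 0 | 0.8 | 1% | 99% |
| 40 | 0.5 | 0 | 0.5 | 3% | 87% |
| 32 | 0.75 | 0 | 0.3 | 12% | 38% |
| 32 | 0.75 | 0 | 0.5 | 22% | 78% |
| 32 | 0.75 | 0 | 0.8 | 42% | 99% |
| 32 | 0.5 | 0.3 | 0 | 37-38% | 4% |
| 32 | 0.5 | 0.5 | 0 | 78% | 3% |

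The last two rows have no TMR effect at all: A-B is then significant because of difficulty alone.

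**The case against.** The strongest reply is that A and B is loose wording for the two sequences. The label definitions come after the four dual-task items, and the objective, the primary outcome and the heading of control comparison 4 all show that replay/no-replay is the contrast of interest. The intent is indeed probably right. But the SAP defines A/B as the labelling that ignores replay, and if the labels were synonyms, control comparisons 1 and 3 would be the same comparison. As written, the four outcomes are on the wrong contrast.

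Several narrower points stand:

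- Relabelling cannot cure uneven replay. If one sequence is always replayed (p = 1), both contrasts are identical and TMR is fully confounded with sequence. At p = 0.75, s = 0.5 and d = 0, replay versus no-replay is still significant in about 22% of runs. That is a matter of how replay is assigned, which the protocol may settle. Having two label systems makes a fixed replayed sequence unlikely.
- Control comparisons 1 and 2 look for an A-B difference before the nap, which gives some protection against reading difficulty as TMR. They give none against missing a TMR effect.
- The simulation is illustrative and leaves out the population factor. With random rather than exact 50:50 replay, A-B is significant in about 5% of runs at each d, which is still no power. The conclusion rests on the formula and does not depend on these percentages.
- The Nap/Wake sentence is a separate defect. It is also the only comparator the section states for single-task retention, so that outcome, though not defined by A/B, needs the sentence corrected too.

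**Conclusion.** The concern holds. Four Experiment 2 secondary outcomes are defined on a contrast that, by the SAP's own label definitions, disregards the intervention, and one of four control comparisons contradicts its heading and duplicates another. Neither finding needs an assumption.

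How much of the TMR effect is lost depends on p: all of it at p = 0.5 and half at p = 0.75. Only at p = 1 does A-B carry the full effect, and there it cannot be separated from difficulty. The rejection rates depend on assumed values of d, s and p.

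The Experiment 2 primary outcome is correctly defined and unaffected. This should be fixed, but it does not threaten the main result.

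**What to change.** - In Dual tasking performance items 1 and 2 and Dual task cost items 1 and 2, define the Experiment 2 contrast as replay versus no-replay.
- In control comparison 4, replace sequence A and sequence B with the replay and the no-replay sequence.
- In the introduction to Secondary outcomes, state that Nap/Wake applies to Experiment 1 and that Experiment 2 outcomes are compared by sequence (replay/no-replay) and population.
- Keep A/B in control comparisons 1 and 2, where it is the right label.
- If replay is not balanced over A and B, add which sequence was replayed as a factor. This separates d from s unless the same sequence is replayed for everyone.

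The cost is a wording change on the same data. According to the note on the amendment of 27 April 2021, nobody had yet been randomized in Experiment 2 when it was submitted. If recruitment has begun since, the change should be dated and made before replay status is linked to the dual-task results.

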Statistical Analysis Plan

Protocol Identification Number: S61792

Brief Title: Role of sleep on motor learning in Parkinson's disease and healthy older adults

Official Title: Boosting motor learning through sleep and targeted memory reactivation in Parkinson's disease and healthy older adults

Acronym: TARGET-SLEEP

Study type: Interventional

Principal Investigator: [name]

Note on protocol amendment 27 April 2021:

It was noted that a formal power calculation was not provided in the original submission on clinicaltrials.gov. The a-priori determined power calculation has now been added. Importantly, the target sample for recruitment did not change to what was noted on the original submission. Moreover, a change was made to the secondary outcomes 7 and 8 regarding dual tasking for experiment 2. It was decided to not have participants perform the dual-task condition during learning, as to minimize learning effects on the primary outcome. Importantly, due to COVID-19 restrictions, recruitment for experiment 2 had not yet commenced and hence no subjects had been randomized prior to submission of this protocol amendment.

Brief summary:

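### In Experiment 2 the dual-task 'offline consolidation' outcome is a Retest 1 difference between sequences with no pre-nap reference; it should be stated as replay minus no-replay, adjusted for end-of-learning PI, and renamed.

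*SAP*

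**What the plan says.** The Experiment 2 primary outcome treats offline consolidation as a pre- to post-nap change: "the change in PI between the first 4 blocks at retest immediately after the nap and the last 4 blocks at learning", compared between the replayed and the non-replayed sequence. In the secondary outcomes, dual-task PI item 1 keeps that idea for Experiment 1: "Offline consolidation measured as the change in PI between the 4 blocks of dual tasking at Retest 1" against the dual-task blocks during learning. For Experiment 2 the same item, under the same name, becomes "differences on PI between sequences A and B during the 4 blocks at Retest 1 for experiment 2".

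The amendment note at the start of the SAP explains the split: "It was decided to not have participants perform the dual-task condition during learning, as to minimize learning effects on the primary outcome". Item 3 of the same list, which limits dual-task learning performance to Experiment 1, confirms that Experiment 2 has no pre-nap dual-task PI. Dual-task cost item 1 has the same structure: for Experiment 2 it is an A-versus-B difference at Retest 1, again called offline consolidation.

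A pre-nap value for each sequence does exist, in single-task form. Control comparison 1 uses "the difference in PI between the last 4 blocks of sequence A and the last 4 blocks of sequence B during learning", and control comparison 3 does the same by replay status: "End of learning performance on the replay and no-replay sequences will be assessed as the difference in PI between the last 4 blocks". The stated purpose is that "four additional comparisons will be analyzed to ensure that participants could learn both sequences equally well". Neither result enters the dual-task outcome.

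**The concern.** A reader who sees a dual-task offline consolidation result for Experiment 2 will take it as a change across the nap, because that is what the term means in the primary outcome and in Experiment 1. Here it is a level after the nap. If one sequence was simply learned better before the nap, part of that advantage will still be present at Retest 1 and will be reported under the consolidation label.

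The choice of labels decides how much this matters. The SAP says A and B are assigned without regard to replay, so an A-versus-B contrast is not a replay contrast. Under replay/no-replay labels with balanced or random choice of the replayed sequence, pre-nap differences average out and cost only precision. If replay is not balanced over the sequences, they bias the estimate. The planned sample is small (20 per population recruited), so lost precision is worth recovering when the covariate is already collected.

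**Working it through.** The plan gives no figure for this outcome to reproduce, so the check is algebra plus calculations under stated assumptions.

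**1. What the contrast contains.** Let L be the end-of-learning PI of a sequence, C its offline gain, and λ the share of a single-task learning difference that carries into dual-task PI. Apart from error and a common dual-task cost, dual-task PI at Retest 1 = λL + C. The between-sequence contrast is therefore

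λ(L₁ − L₂) + (C₁ − C₂).

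Only the second term is consolidation. The definition removes none of the first. The SAP does not give λ.

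**2. Size under A-versus-B labels.** Simulation, 4,000 runs, n = 20. Assumed: subject SD 8, per-sequence learning SD 3, dual-task error SD 2, error SD 1 on measured end-of-learning PI, a 2-point A−B learning difference and no replay effect.

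| λ | Mean of A−B at Retest 1 (should be 0) | Rejections |
|---|---|---|
| 1 | 2.0 | about 39% |
| 0.7 | 1.4 | about 31% |
| 0.4 | 0.8 | about 17% |

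For scale, by the SAP's PI formula with an assumed 1 error per block, 0.1 s of sequence duration is worth 100 × (e^−0.9 − e^−1.0) × e^(−1/12) = 3.6 points at 0.9 versus 1.0 s, and 5.3 points at 0.5 versus 0.6 s. A 2-point difference is thus small.

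With balanced replay, no learning difference and a true 2-point replay effect, the A−B mean is 0.0: the effect cancels. Adding a covariate without changing the labels would not rescue the item.

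**3. Replay minus no-replay, adjusted for end-of-learning PI.** Same assumptions, no replay effect: with balanced replay the mean is 0.0 and rejection about 5%. With unbalanced replay a residual of 0.1 to 0.2 remains, with 5–6% rejection. Subtracting the single-task baseline instead is exact only at λ = 1; with unbalanced replay it over-corrects by 0.6 points at λ = 0.7 and 1.2 at λ = 0.4. Regression estimates λ rather than fixing it at 1.

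**4. Precision when replay is balanced.** Let r be the correlation between the end-of-learning and Retest 1 between-sequence differences (assumed). The large-sample standard-error ratio is √(1 − r²): 0.866 at r = 0.5 and 0.714 at r = 0.7, reductions of 13% and 29%. Simulated power for an assumed replay effect of dz = 0.5:

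| n | Unadjusted | r = 0.5 | r = 0.7 | r = 0 |
|---|---|---|---|---|
| 16 (one population after dropout) | 47% | 55% | 71% | 44% |
| 40 (both populations as recruited) | 87% | 94% | 99% | 86% |

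Type I error stays at about 5%. With centred population in the model, the n = 40 results agree.

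**5. Protection from the control comparisons.** Paired-t power to detect a 0.5 SD learning difference is 0.47 at n = 16, 0.57 at n = 20 and 0.87 at n = 40. Within one population, a non-significant check says little.

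**The case against.** The strongest reply is that this is mostly a preference for covariate adjustment. The amendment note says no subjects had yet been randomised in Experiment 2. Since all its participants nap and only the replayed sequence differs, the replayed sequence is the natural thing to randomise. The SAP does not say so, but such detail normally sits in the protocol, which is not at hand. If it is randomised, the unadjusted replay contrast is valid, and its standard error already covers chance differences in learning. That stands: nothing in the SAP shows an unbalanced choice, and bias in the replay contrast cannot be asserted.

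A reader might also infer that the whole pre-nap difference passes into the outcome. The SAP does not support that. The baseline is single-task on a cued task, and the retest is dual-task without cues. One-for-one carry-over (λ = 1) is an assumption; at λ = 0.4 the carry-over is less than half.

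Dropping the dual task from learning was deliberate, disclosed and reasoned, and is not the fault. The plan also does look at the learning difference. What survives is that the name no longer fits, the contrast as written is A versus B, and the available baseline is tested but not used. Dual-task cost does not fill the gap, because at Retest 1 it subtracts single-task PI from after the nap.

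**Conclusion.** The point holds in limited form. The Experiment 2 part of dual-task PI item 1, and of dual-task cost item 1, is a Retest 1 difference under a label that the SAP otherwise uses for a change from learning. Pre-nap learning differences enter the PI item in proportion to λ: as noise under replay labels with balanced or random choice, and as bias under A-versus-B labels or unbalanced choice.

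Adjustment gains about 7 to 12 percentage points of power at n = 40 and loses about 1 if the baseline is uninformative. These figures rest on assumed dz = 0.5, r between 0 and 0.7, and no dropout; the SAP supplies none of the effect sizes or correlations. The outcome is secondary and the primary analysis is untouched, so this is worth doing but minor.

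**What to change.** For Experiment 2, dual-task PI item 1:

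- State the contrast as replay minus no-replay in dual-task PI over the 4 blocks at Retest 1.
- Fit D = α + βL + γP + error, where D is each participant's replay minus no-replay dual-task PI, L is the same difference in single-task PI over the last 4 Learning blocks, and P is population coded +½ and −½. Then α is the replay effect at zero pre-nap difference, averaged over the two populations, and γ is the population difference in that effect. With 0/1 coding α would describe only the reference population, so the coding must be written down.
- Rename the item, for example 'dual-task performance after replay, adjusted for end of learning'.
- Rename the Experiment 2 part of dual-task cost item 1 as well, so that no Retest 1 difference keeps the consolidation label.

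The cost is SAP wording and one degree of freedom for a covariate already collected, with a slight loss of precision if the correlation is near zero. No new data are needed.
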